11 DATA AND SAFETY MONITORING PLAN (DSMP)

11.1 Data and Safety Management Overview

The Medical College of Wisconsin (MCW) Data Safety Monitoring Committee (DSMC) and the MCW Institutional Review Board (IRB) will approve protocol-specific DSM plans described below. A local, investigator-initiated trial will be required to be continuously monitored by the principal investigator of the study with regular safety and progress reports submitted to the DSMC.

The DSMP for this study will involve the following entities:

11.2 Study Team

The study team minimally consists of the principal investigator, the clinical research coordinator, regulatory specialist and the study biostatistician. While patients are on treatment, the principal investigator will meet regularly with the research coordinator and the study biostatistician to review study status. This review will include but not be limited to reportable SAEs and UPIRSOs and an update of the ongoing study summary that describes study progress in terms of the study schema. The appropriateness of further subject enrollment and the specific intervention for a next subject enrollment is addressed. All meetings including attendance are documented.

11.3 Quality Assurance

The MCWCC Clinical Trials Office provides ongoing quality assurance audits Intermediate risk trials are reviewed every year

- 20% of subject files will be selected randomly for review (a maximum of 10 subjects at each monitoring time point). Consent/eligibility and objective-based data will be reviewed for those files selected.
- One file will be selected randomly for a comprehensive review at each monitoring time point.
- Regulatory documents (IRB submissions, reportable events, etc.) will be reviewed at each monitoring time point.

11.4 Clinical Trials Office

The MCWCC Clinical Trials Office [CTO] provides administrative assistance and support to the DSMC.

11.5 DSMC

The Medical College of Wisconsin Cancer Center places the highest priority on ensuring the safety of patients participating in clinical trials. Every cancer interventional trial conducted at MCW includes a plan for safety and data monitoring.

This study will be reviewed by the Medical College of Wisconsin Cancer Center Data and Safety Monitoring Committee (MCWCC DSMC). A summary of the MCWCC DSMC activities are as follows:

- Review the clinical trial for data integrity and safety
- Review all unexpected grade 3, and all grade 4, and 5 adverse events, as well as any others requiring expedited reporting as defined in this protocol. (Grades 4 & 5 events must be reported to the DSMC within 5 calendar days of study staff's knowledge.)
- Review all DSM reports
- Submit a summary of any recommendations related to study conduct
- Terminate the study if deemed unsafe for patients

A copy of the MCWCC Data and Safety Monitoring Plan and membership roster will be maintained in the study research file and updated as membership changes. The committee will review reports from the study PI twice annually (or more frequently if needed) and provide recommendations on trial continuation, suspension or termination as necessary.

Any available DSMC letters will be submitted to the IRB of record as required.

12 REGULATORY COMPLIANCE, ETHICS AND STUDY MANAGEMENT

12.1 Ethical Standard

This study will be conducted in accordance with the ethical principles that have their origin in the Declaration of Helsinki as stated in 21 CFR 312.120(c)(4); consistent with GCP and all applicable regulatory requirements.

12.2 Regulatory Compliance

This study will be conducted in compliance with:

- The protocol
- Federal regulations, as applicable, including: 21 CFR 50 (Protection of Human Subjects/Informed Consent); 21 CFR 56 (Institutional Review Boards) and §312 (Investigational New Drug Application; and 45 CFR 46 Subparts A (Common Rule), B (Pregnant Women, Human Fetuses and Neonates), C (Prisoners), and D (Children), GCP/ICH guidelines, and all applicable regulatory requirements. The IRB must comply with the regulations in 21 CFR §56 and applicable regulatory requirements.

12.3 Institutional Review Board

The protocol, the proposed informed consent form and all forms of participant information related to the study (e.g. advertisements used to recruit participants) will be reviewed and approved by the MCW Institutional Review Board. Prior to obtaining MCW approval, the protocol must be approved by the Medical College of Wisconsin Cancer Center Scientific Review Committee. The initial protocol and all protocol amendments must be approved by the IRB prior to implementation.

12.4 Informed Consent Process

Informed consent is a process that is initiated prior to the individual's agreeing to participate in the study and continues throughout the individual's study participation. Extensive discussion of risks and possible benefits of this therapy will be provided to the subjects and their families. Consent forms describing in detail the study interventions/products, study procedures and risks

are given to the subject and written documentation of informed consent is required prior to starting intervention/administering study product.

Consent forms will be IRB-approved and the subject (and Legally Authorized Representative, if necessary) will be asked to read and review the document. Upon reviewing the document, the investigator will explain the research study to the subject and answer any questions that may arise. In accordance with 46 CR 46.111, the subject will sign and date the informed consent document prior to any procedures being done specifically for the study.

Subject confidentiality is strictly held in trust by the sponsor-investigator, participating investigators, and any staff. This confidentiality includes the clinical information relating to participating subjects, as well as any genetic or biological testing.

The study protocol, documentation, data, and all other information generated will be held in strict confidence. No information concerning the study or the data will be released to any unauthorized third party without prior written approval of the principal investigator.

The conditions for maintaining confidentiality of the subjects' records are required for the life of the data. These rules apply equally to any and all MCWCC projects.

12.5 Prestudy Documentation

Prior to implementing this protocol at MCWCC, the protocol, informed consent form, HIPAA authorization and any other information pertaining to participants must be approved by the MCW IRB.

The clinical investigation will not begin until either FDA has determined that the study under the Investigational Drug Application (IND) is allowed to proceed or the Investigator has received a letter from FDA stating that the study is exempt from IND requirements.

12.6 Protection of Human Subjects

Protection from Unnecessary Harm

Each clinical site is responsible for protecting all subjects involved in human experimentation. This is accomplished through the IRB mechanism and the informed consent process. The IRB reviews all proposed studies involving human experimentation and ensures that the subject's rights and welfare are protected and that the potential benefits and/or the importance of the knowledge to be gained outweigh the risks to the individual. The IRB also reviews the informed consent document associated with each study in order to ensure that the consent document accurately and clearly communicates the nature of the research to be done and its associated risks and benefits.

Protection of Privacy

As noted, patients will be informed of the extent to which their confidential health information generated from this study may be used for research purposes. Following this discussion, they will be asked to sign informed consent documents. The original signed document will become part of the patient's medical records, and each patient will receive a copy of the signed document.

12.7 Investigator Compliance

The investigator will conduct the study in compliance with the protocol given approval/favorable____

opinion by the IRB and the appropriate regulatory authority(ies).

12.8 Onsite Audits

Auditing is essential to ensure that research conducted at the Medical College of Wisconsin (MCW) Cancer Center is of the highest quality and meets MCW and regulatory agency standards.

Regulatory authorities, the IRB and/or sponsor may request access to all source documents, data capture records and other study documentation for on-site audit or inspection. Direct access to these documents must be guaranteed by the investigator, who must provide support at all times for these activities.

13 DATA HANDLING AND RECORD KEEPING

13.1 Overview

Every effort is made to uphold the integrity of the project, the research, the institution, and the researchers involved. Data collection guidelines and methodologies are carefully developed before the research begins. Investigators focus on the following to ensure data integrity: well-trained data collectors/recorders to ensure consistency and quality, well-designed data collection protocols and ongoing monitoring. In this way, study rigor and validity are maintained. Data is protected from physical damage as well as from tampering, loss or theft. This project's data management is a multidisciplinary activity that includes investigators, research coordinators and nurses, data mangers, support personnel, biostatisticians and database programmers. Quality control will be applied to each stage of data handling to ensure that all data are reliable and have been processed correctly.

13.2 Case Report Forms

The principal investigator and/or his/her designee will prepare and maintain adequate and accurate participant case histories with observations and data pertinent to the study. Study-specific Case Report Forms (CRFs) will document safety and treatment outcomes for safety monitoring and data analysis. All study data will be entered into OnCore[®] via standardized CRFs, in accordance with the study calendar, using single data entry with a secure access account.

All source documentation and data will be available for review/monitoring by the MCWCC DSMC and regulatory agencies.

13.3 Handling and Documentation of Clinical Supplies

The Investigational Pharmacy will maintain complete records showing the receipt, dispensation, return, or other disposition of black raspberries. The date, quantity and batch or code number of the agent, and the identification of patients to whom study drug has been dispensed by patient number and initials will be included. The sponsor-investigator will maintain written records of any disposition of the study drug.

The principal investigator shall not make the agent available to any individuals other than to qualified study patients. Furthermore, the principal investigator will not allow the agent to be used in any manner other than that specified in this protocol.

13.4 Study Record Retention

The principal investigator is required to maintain adequate records of the disposition of the drug, including dates, quantity and use by subjects, as well as written records of the disposition of the drug when the study ends.

In accordance with FDA regulations, the investigator shall retain records for a period of two years following the date a marketing application is approved for the drug for the indication for which it is being investigated; or, if no application is to be filed or if the application is not approved for such indication, until two years after the investigation is discontinued and FDA is notified.

APPENDIX 1. PERFORMANCE STATUS CRITERIA

ECOG Performance Status Scale		Karnofsky Performance Scale			
Grade	Descriptions	Percent	Descriptions		
0	Normal activity Fully active, able to carry on all	100	Normal, no complaints, no evidence of disease		
	pre-disease performance without restriction	90	Able to carry on normal activity; minor signs or symptoms of disease		
1	1 Symptoms, but ambulatory Restricted in physically strenuous activity, but		Normal activity with effort; some signs or symptoms of disease		
	ambulatory and able to carry out work of a light or sedentary nature (e.g. , light housework, office work)	70	Cares for self, unable to carry on normal activity or to do active work		
2	 In bed < 50% of the time Ambulatory and capable of all self-care, but unable to carry out any work activities Up and about more than 50% of waking hours 		Requires occasional assistance, but is able to care for most of his/her needs		
			Requires considerable assistance and frequent medical care		
3	3 In bed > 50% of the time		Disabled, requires special care and assistance		
	care, confined to bed or chair more than 50% of waking hours	30	Severely disabled, hospitalization indicated		
			Death not imminent		
4	100% bedridden Completely disabled	20	Very sick, hospitalization indicated Death not imminent		
Cannot carry on any self-care Totally confined to bed or chair		10	Moribund, fatal processes progressing rapidly		
5	Dead	0	Dead		

APPENDIX 2. MODIFIED IWG RESPONSE CRITERIA

Hematologic	Response Criteria (responses must last at least 8 weeks)				
Improvement (HI)					
Erythroid response	- Hgb increase by ≥ 1.5 g/dL.				
(pretreatment, < 11 a/dL)	- Relevant reduction of RBC transfusion units by an absolute				
. ,	number of at least 4 RBC transfusions/8 wk compared with				
	the pretreatment transfusion number in the previous 8 wk.				
	- Only RBC transfusions given for an Hgb of \leq 9.0 g/dL				
	pretreatment will count in the RBC transfusion response				
	evaluation.				
Platelet response	- Absolute increase of \geq 30 x 109/L for patients starting with				
(pretreatment, < 100 x 109/L)	> 20 x 109/L platelet.				
	- Increase from < 20 x 109/L to > 20 x 109/L and by at least				
	100%.				
Neutrophil	At least 100% increase and an absolute increase > 0.5 x 109/L.				
response (pretreatment					
< 1.0 x 109/L)					
Progression or	At least one of the following:				
relapse after HI	- At least 50% decrement from maximum response levels in				
	aranulocytes or platelets				
	= Reduction in Hab by > 1.5 a/dl				
	- Reduction in rigb by ≥ 1.5 g/dE.				
	- i ransiusion dependence in transfusion independent				
	patients.				

Category	Response criteria (responses must last at least 4 weeks)
Complete remission	Bone marrow: ≤ 5% myeloblasts with normal maturation of all cell lines Persistent dysplasia will be noted
	Peripheral blood: Hgb \geq 11 g/dL Platelets \geq 100 × 10 ⁹ /L Neutrophils \geq 1.0 × 10 ⁹ /L Blasts 0%
Partial remission	All CR criteria if abnormal before treatment except: Bone marrow blasts decreased by ≥ 50% over pretreatment but still > 5% Cellularity and morphology not relevant
Marrow CR	Bone marrow: $\leq 5\%$ myeloblasts and decrease by $\geq 50\%$ over pretreatment
	Peripheral blood: if HI responses, they will be noted in addition to marrow CR
Stable disease	Failure to achieve at least PR, but no evidence of progression for > 8 weeks.
Failure	Death during treatment or disease progression characterized by worsening of cytopenias, increase in percentage of bone marrow blasts, or progression to a more advanced MDS FAB subtype than pretreatment
Cytogenetic response	Complete: Disappearance of the chromosomal abnormality without appearance of new ones Partial: At least 50% reduction of the chromosomal abnormality
Disease Progression	 For patients with: Less than 5% blasts: ≥ 50% increase in blasts to > 5% blasts 5%-10% blasts: ≥ 50% increase to > 10% blasts 10%-20% blasts: ≥ 50% increase to > 20% blasts 20%-30% blasts: ≥ 50% increase to > 30% blasts
	 Any of the following: At least 50% decrement from maximum remission/response in granulocytes or platelets Reduction in Hgb by ≥ 2 g/dL Transfusion dependence

World Health Organization (WHO) Classification-Based Prognosis Scoring System (WPSS calculator): http://www.myelodysplastischesyndrome.de/service/wpss_kalkulator/

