4.1 Inclusion Criteria

A potential subject must meet all the following inclusion criteria to be eligible to participate in the study.

1. Patients must have a confirmed diagnosis of myelodysplastic syndrome or myelodysplastic syndrome/ myeloproliferative neoplasms (MDS/MPN) proven by bone marrow biopsy/aspirate.

- 2. Patients with cytopenias (blood cell counts lower than the institutional lower limit of normal within the eight weeks prior to the study) who are receiving or received:
 - red blood cell transfusions
 - observation
 - platelet transfusions
 - erythropoietin
 - granulocyte colony-stimulating factors
 - granulocyte-macrophage colony-stimulating factors
 - hydrea
- 3. Age >18 years.
- 4. Predicted life expectancy of at least 12 weeks.
- 5. Patients should be expected to stay on the same therapy for the period of the study.
- 6. Patients who do not have an indication for and/or are believed to be unable to tolerate a hypomethylating agent are eligible for the study.
- 7. Reproductive requirements:

Female patients must meet one of the following:

- Postmenopausal for at least one year before the screening visit, or
- Surgically sterile, or
- If they are of childbearing potential, agree to practice two effective methods of contraception from the time of signing of the informed consent form through 30 days after the last dose of study drug, AND
- Must also adhere to the guidelines of any treatment-specific pregnancy prevention program, if applicable, or
- Agree to practice true abstinence when this is in line with the preferred and usual lifestyle of the subject. (Periodic abstinence [e.g., calendar, ovulation, symptothermal, postovulation methods] and withdrawal are not acceptable contraception methods.)

Male patients, even if surgically sterilized (i.e., status postvasectomy), must agree to one of the following:

- Practice effective barrier contraception during the entire study treatment period and through 30 days after the last study drug dose, OR
- Must also adhere to the guidelines of any treatment-specific pregnancy prevention program, if applicable, OR
- Agree to practice true abstinence when this is in line with the preferred and usual lifestyle of the subject. (Periodic abstinence [e.g., calendar, ovulation, symptothermal, postovulation methods] and withdrawal are not acceptable methods of contraception.)
- 8. Ability to understand a written informed consent document, and the willingness to signit.

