6.3 General Concomitant Medication and Supportive Care Guidelines

The treating physician will use standard supportive care to control symptoms and improve quality of life. These may include:

- Transfusions
- Use of growth factors
- Antibiotics

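### Appendix 2 counts transfusion dependence as progression without a baseline qualifier, so a stable patient dependent at entry can be misclassified as progressed at cycle 4

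*Combined protocol and SAP*

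**What the plan says.** Appendix 2 treats transfusion dependence in two places, and the two differ.

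- **Disease Progression row.** After the blast-increase items comes a list of which any one suffices. It ends with "Transfusion dependence". There is no reference period, no requirement that the dependence be new, and no limit on which patients it applies to.
- **Progression or relapse after HI.** Here the item is transfusion "dependence in transfusion independent" patients, so baseline status is part of the criterion.

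The appendix does not define dependence by number of units.

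The Disease Progression row matters for treatment in two ways. Stable disease is "Failure to achieve at least PR, but no evidence of progression for" more than eight weeks, and Section 3.1 and Study Calendar footnote 12 accept stable disease without progression as enough to continue past the C4D1 assessment. Section 5.6 makes progression under Appendix 2 a reason to end treatment.

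Eligibility brings transfused patients in. Section 4.1, criterion 2, lists patients on "red blood cell transfusions" and on platelet transfusions. Criterion 5 adds: "Patients should be expected to stay on the same therapy for the period of the study". Section 6.3 says "The treating physician will use standard supportive care to control symptoms and improve quality of life", and names transfusions as an example.

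**The concern.** Continued transfusion is the expected course for a patient who enters transfusion dependent and does not respond. A criterion that counts the state itself, rather than a change into it, labels that patient as progressed when nothing has worsened.

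Two things are at stake. The first is treatment: the Background section allows six cycles before patients without CR, PR or HI stop, and a literal reading shortens this to three for patients dependent at entry. The second is classification: the same unchanged patient could be called stable by one assessor and progressed by another, because the two rows differ and dependence has no threshold.

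**Working it through.** The plan gives no figure on this point to reproduce: neither the share of patients dependent at entry nor a unit threshold is stated. The sample-size calculation in Section 10 does not enter. The check is a reading of the text followed by simple counts.

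**Reading, step by step**

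1. A patient dependent on red cell transfusions is eligible (Section 4.1, criterion 2).
2. C4D1 falls 3 × 28 = 84 days, or 12 weeks, after C1D1. The condition of more than eight weeks for stable disease can therefore be met by then.
3. Suppose the patient is unchanged: no CR, PR or HI, no blast rise, no fall in counts, same transfusion need.
4. Dependence is still present, so the item in the Disease Progression row is met on its words.
5. Stable disease is then excluded, because it requires no evidence of progression.
6. The patient is not benefiting under Section 3.1 and meets the Section 5.6 reason for stopping.

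Step 4 assumes that the blast items and the list after them are alternatives. The row as read shows no *and* or *or* between them. Alternatives is the natural reading, and the Study Calendar schedules no marrow examination on treatment, which would make a joint requirement hard to apply. If both parts were required, the patient in step 3 would not have progressed.

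**Size per affected patient** (stable throughout, no CR, PR or HI by C7D1)

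- Treatment lost: cycles 4 to 6 = 3 × 28 = 84 days. At two doses a day, 84 × 2 = 168 doses. This is a ceiling: on the once-daily reduction in Section 6.2 it would be 84. Without a response the patient would stop at C7D1 anyway.
- Methylation samples through C7: C1, C2, C3, C4 and C7 = 5. Stopping at C4D1 leaves 4, so one is lost. The C4 sample is due at that same visit, and the end-of-treatment sample is still taken.
- Section 10 plans four comparisons with baseline for each of six genes (4 × 6 = 24) without naming the four times. If they are C2, C3, C4 and C7, the C7 comparison is the one that loses data.
- Classification: the patient has completed three cycles and is evaluable for response under Section 9.1. One patient of 18 is 1/18 = 5.6%, taken from stable disease and added to progression.
- Response at C4: the Background section defines response as CR, PR or HI. Neither stable disease nor progression is a response, so relabelling changes the rate by 0 points.

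A patient who would first have responded in cycles 4 to 6 forgoes that response, which bears on the best-clinical-response endpoint (Sections 3.4 and 9.4). The documents give no rate for this under black raspberries.

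**Number affected.** Not given; anything from 0 to 18 of 18 fits the eligibility criteria.

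**The case against.** The strongest reply is that the literal reading defeats itself. If no change is needed, an eligible transfusion-dependent patient has progressed on C1D1, before the first dose. The surrounding text also points to change. The other items in the row are a rise in blasts, a decrement from best response and a fall in hemoglobin. The Failure row speaks of "disease progression characterized by worsening of cytopenias". The erythroid HI row credits a reduction by an absolute "number of at least 4 RBC transfusions/8 wk compared with" the pretreatment eight weeks, so transfused patients are judged against their own baseline. Footnote 13 collects exactly that history.

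Most of this stands as evidence of intent: new dependence was probably meant. It does not settle the text. The Failure row is a separate category and does not amend the Disease Progression row. The presence of the qualifier in the relapse-after-HI row lets a reader take its absence elsewhere as deliberate.

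It is also fair to say that stable-disease and progression rates are not named endpoints, and that Section 10 assumes data missing at random and keeps patients with partial data. Both points limit the damage without removing the early stop.

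A reader might infer that every transfusion-dependent patient will be taken off treatment at C4. The documents do not support that: the unit threshold is undefined, the link between the two parts of the row is unstated, and the intended meaning is probably different. A reader might also infer that HI responders who remain dependent lose treatment. For them the row conflicts with the relapse-after-HI row and with HI counting as benefit at C4, so the text does not clearly require stopping.

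**Conclusion.** The point holds as an inconsistency in a rule that governs stopping and classification. It is open to misapplication and is not certain to force anyone off treatment. Where the row is applied literally, with its two parts as alternatives, each stable patient dependent at entry loses up to three cycles and the C7 methylation sample, and shifts the stable-disease and progression counts by one (5.6 points each if all 18 are evaluable).

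The C1 to C4 methylation comparison, which serves the three-cycle primary objective, is unaffected. So are the CR/PR/HI rate at C4 and any best response already reached. A loss of power at C7 might be inferred, but it cannot be stated, because it would rest wholly on an assumed share of dependent patients. The repair is worth making because it is cheap and the rule ends treatment.

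**What to change.** Reword the item in the Disease Progression row as: *new transfusion dependence in patients not transfusion dependent in the eight weeks before C1D1*, judged against the history collected under Study Calendar footnote 13. The investigator should set one unit threshold for dependence and use it both before entry and on treatment, so that an occasional pre-entry transfusion does not exempt a patient from the criterion. The rewording also removes the conflict with the relapse-after-HI row.

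Patients dependent at entry would then have no transfusion-based progression item. If one is wanted, use an investigator-set rise in units per eight weeks over the pretreatment eight weeks.

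Section 10 reports seven patients already through three cycles, so any C4 classifications already made should be checked against the clarified wording.

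The cost is one line in Appendix 2 plus the clinical choice of the threshold and, if adopted, of the rise. No new data or visits are needed.
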